### 3.2. Study design

Two-arm cluster-randomized controlled trial (cRCT) to test effect of a model of peer PrEP referral enhanced with training and HIVST delivery compared to informal word-of-mouth peer PrEP referral (i.e., the existing standard) on PrEP initiation among Kenyan AGYW:

**Figure 1. Study groups for the Peer PrEP cRCT.**

### 3.3. Eligibility criteria

The eligibility criteria for trial participants and recruitment strategies are described below in **Table 2**.

**Table 2. Eligibility criteria for index peers and referred peers in the Peer PrEP cRCT**

[figure not shown]
	Eligibility	Ineligibility	Recruitment strategies
Index peers (n=80)	
 
• <math>\geq 16</math>- 24 years old*
 
• Female
 
• Must have refilled or initiated PrEP (i.e., been dispensed PrEP).
 
• Not currently enrolled in a HIV study
 
• Can identify 4 peers at HIV risk who could benefit from PrEP.
 
• Able & willing to be randomized to the intervention, participate in research activities, and/or provide written informed consent
 
	
 
• Not between 16-24 years old
 
• Male
 
• Have not used PrEP.
 
• Cannot identify 4 peers who would benefit from PrEP.
 
• Is not able or willing to be randomized to the intervention, participate in research activities, and/or provide written informed consent.
 
• Currently enrolled in a HIV study.
 
• Illiterate
 
	
 
• Recruit participants from HIV clinics where PrEP is available using PHRD recruitment strategies (e.g., workshops for healthcare workers).
 
• Strategies developed and refined during the pilot study.
 

Referred peers (n=320)	
 
• Age <math>\geq 16</math> to 24 years
 
• Female
 
• Referred by index peer to initiate PrEP.
 
• Able & willing to provide informed consent.
 
	
 
• Age <math><16</math> or <math>>24</math> years
 
• Male
 
• Not referred by index peer to initiate PrEP
 
• Not able or willing to provide informed consent.
 
	
 
• Index peers will recruit referred peers. At point of recruitment, referred peers will call research staff to provide contact info for follow-up.
 
• (IRB modification): At follow-up, index peers share the contact information of peers referred so they can be reached for follow-up.
 
• If referred peer calls the study staff, both the referred peer and index peer will be compensated 150 KES via mobile money.
 

\* To minimize risks to minors, we will only enroll young women  $\geq 16$  to 17 years into the study if they are emancipated minors and thus able to legally provide consent for participation in research. Kenyan law acknowledges women ages 14 to 17 who have become pregnant as emancipated minors

This IRB modification was implemented after few referred peers contacted the research team to share their contract information. It was approved 6-months in to cRCT implementation in November 2023.

### **3.4. Study procedures**

The overview of study procedures—including interventions and data collection activities—by study group is detailed in **Figure 2**.

## Figure 2. Overview of study procedures.

#### 4. Study endpoints

We have registered all Peer PrEP cRCT outcomes on ClinicalTrials.gov (ID: NCT04982250) (2).

#### **4.1. Primary & secondary PrEP outcomes**

Our primary trial outcome will be PrEP initiation among referred peers, as reported by Index peers at the 3-month follow-up visit, **Table 3**. We will categorize clients as having initiated PrEP if they went to a healthcare facility (or other location) and were dispensed PrEP pills—consistent with how PrEP initiation is being measured in other PrEP implementation studies. We will also measure several secondary outcomes, including recent HIV testing, PrEP continuation, and PrEP adherence.

We are measuring all outcomes at 3 months to give referred peers time to both link to care, initiate PrEP services, and complete their first PrEP refill one month later if they are interested in continuing services. Additionally, this period is close enough to when the intervention was delivered that we anticipate little recall bias. Because we had challenges following up with referred peers in the pilot study leading up to this cRCT, we will be measuring all primary outcomes and most secondary outcomes reported by index peers, who are easier to follow-

up with and will report outcomes on behalf of the peers they recruited, as is typically done in interventions that utilize secondary distribution models. However, we will do our best to follow-up with referred peers and will measure our PrEP adherence outcomes reported from this population (we will also measure our primary and other secondary outcomes reported among this population and report them in sensitivity analyses).

Retention window (3 months): While most participants return for follow-up close to the scheduled 3-month visit date, operationally the scheduling window for this visit opens 2 weeks prior this scheduled visit date and closes 2 weeks after the scheduled date, unless a longer window was specifically requested by the participant. For our primary analysis, we will use follow-up visits assigned as 3-month visits by study staff.

**Table 3. Detailed description of Peer PrEP cRCT primary and secondary outcomes**

Outcome	Definition	Reported by	Timing
PrEP initiation*	% of referred peers that went to a clinic and were dispensed PrEP pills , among those referred	Index peers*	Month 3
Recent HIV testing	% of referred peers who tested for HIV (any form of testing, including HIVST) since peer PrEP referral, among those referred.	Index peers	Month 3
PrEP continuation	% of referred peers that returned to a clinic to refill PrEP , among those referred. 	Index peers	Month 3
	% of index peers that returned to a clinic to refill PrEP , in the past 3 months (i.e., since peer referral)	Index peers	Month 3
PrEP adherence	Median of Wilson et al's 0-100 point adherence score,  with higher scores indicating higher adherence 	Referred peers	Month 3

\* Primary outcome

In prior versions of the SAP (v1.5), this was conditional among clients who initiated PrEP, but we changed to make it unconditional to align with the intent-to-treat analysis plan (described below) and best RCT practices on 07/11/2024—prior to study unblinding—per the recommendation of our DSMB.

Wilson, I. B., et al. (2009). "Improving the self-report of HIV antiretroviral medication adherence: is the glass half full or half empty?" *Curr HIV/AIDS Rep* 6(4): 177-186.

In prior versions of this SAP (v1.4), we had suggested an adherence threshold based on the Wilson et al score, but on 3/22/2024—prior to study unblinding—we decided to turn this into a continuous outcome after observing low continuation and thus low adherence in the past month among referred peers in review of the aggregate data across study arms in our DSMB.

#### 4.2. Process outcomes

We will also measure several process outcomes and compare these between the different study groups to help us better understand our primary and secondary outcomes. These process outcomes include: number of peers referred, HIVST use (enhanced group only), and

linkage to care among other relevant outcomes. The details for how we will measure these outcomes are described in **Table 4**; we will measure these outcomes among both index and referred, where appropriate.

**Table 4. Detailed description of Peer PrEP cRCT process outcomes**

Process outcomes	Definition	Reported by	Timing
Peers referred	Number clients referred to PrEP services by index peers	Index peers	Month 3
HIVST use	% of referred peers in the enhanced group that used an HIVST (once; twice; or for partner testing)	Referred peers	Month 3
Client linkage to care	% of referred peers that went to a clinic to access HIV prevention/treatment services, among those referred	Referred peers	Month 3

Note: All outcomes binary.

#### **4.3. Implementation outcomes**

We will measure acceptability, appropriateness, and feasibility of the PrEP referral + HIVST delivery model among index peers and referred peers at Month 3. To measure these outcomes, we will use questions based on validated theories and frameworks, including the Acceptability of Intervention Measure, Intervention Appropriateness Measure, and Feasibility of Intervention Measure (5, 6). See **Table 5** for more details on measurement of these outcomes.

**Table 5. Detailed description of Peer PrEP cRCT implementation outcomes**

Implementation outcome	Definition	Timing
Acceptability	% of referred peers & index peers who report our intervention model is acceptable using validated scales .	Months 3
Appropriateness	% of referred peers & index peers who report our intervention model is appropriate using validated scales .	Months 3
Feasibility	% of referred peers & index peers who report our intervention model is feasible using validated scales .	Months 3
Fidelity	% of referred peers reporting receiving the different intervention materials (e.g., educational brochure, 2 HIVST kits, and Kenya Ministry of Health referral card)	Month 3

[figure not shown]
#### **5. Sample size justification**

##### **5.1. Sample size calculation**

If we assume that index peers refer 75% of suggested referred peers, this leaves us with three clients per peer provider, or 240 referred peers in total. We performed power calculations for our primary outcome, the proportion of referred peers who initiated PrEP at three months, in Stata 16.1 using methods for cluster-randomized trials (cRCTs), where each cluster is a peer group of one index peer and three referred peers.

**Table 6** and **Figure 3** shows the power we attain to detect various increases in the proportion of referred peers who initiated PrEP in the enhanced group versus the standard. For our power calculations, we assumed 40 clusters (index peers) per group, 3 sampling units (referred peers) per cluster, and an intra-cluster correlation coefficient (ICC) of 0.05, which is standard for cRCTs, we might have 80% power to detect a difference of 17% PrEP initiators between the enhanced group (80%) and standard group (63%).

**Figure 3. Power calculation to detect increase in the percentage of referred peers initiating PrEP in the enhanced group compared to the standard.**

**Table 6. Increase in the % of referred peers initiating PrEP in the enhanced group compared to standard under different assumptions.**

Power	Standard: % PrEP initiation	Enhanced: % PrEP initiation	% increase
80%	57.1%	75.0%	17.7%
	63.0%	80.0%	17.0%
	69.1%	85.0%	15.7%
85%	55.8%	75.0%	19.2%
	61.7%	80.0%	18.3%
	67.9%	85.0%	17.10%
90%	54.2%	75.0%	20.8%
	60.1%	80.0%	19.9%
	66.4%	85.0%	18.7%

Assumptions: ICC: 0.05; clusters (providers) per arm: 40; units (clients) per cluster: 3 (75% of suggested clients referred)

## 6. Randomization and masking

## **6.1. Randomization**

Randomization list. A Fred Hutch statistician will prepare a list of randomization assignments for index peers with block sizes of 4. This list will be stored in a password-protected electronic file on a Fred Hutch server.

Randomization implementation. Index peers will be randomized at enrollment, which will occur at Month 0. Then, referred peers will be chosen by index peers. At the time of randomization, index peers will open an opaque randomization envelope, given to them by a study research assistant, that has their study arm assignment inside.

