684 follow-up questionnaires are conducted via phone. All peer providers will be encouraged to disclose PrEP
685 use to peers, although this is not required. Study counselors will conduct follow-up calls with peer
686 providers to check in and see how the referral process is going and answer any questions or concerns
687 regarding the intervention. Recruitment of peer providers will be on a rolling basis, so it is possible that
688 peer providers and peer clients may not be mutually exclusive (as future peer providers could be previous
689 peer clients).

690 *Peer clients.* Peer providers will recruit peer clients. Peer clients will contact study counselors (via phone),
691 to provide RAs with contact information to schedule a follow-up visit (Month 3) at the PHRD study site
692 (transport refunded) or via phone interview. Clients won't be engaged in study activities at Month 3 until
693 they have provided informed consent. To help prompt peer providers to remind peer clients to call
694 research staff at the point of recruitment (a challenge during the pilot study), we will compensate peer
695 providers and their peer clients a small amount (150 KES each, ~\$1.40 USD each) each time a peer
696 client pings the study phone line to enroll in the study. For any peer clients who do not ping the study
697 phone, study staff will attempt to collect contact information for the peer clients from the peer providers
698 during a follow-up visit/call. The peer client can still decline enrollment when contacted by study staff.
699 Peer clients will be compensated 300 KES (~\$2.70 USD) and reimbursed for travel for attending the 3-
700 month follow-up appointment. No travel reimbursement will be provided if the questionnaires are
701 conducted over the phone. To facilitate the delivery of this compensation, we will use a secure mobile
702 money platform (M-Pesa) that we have used successfully for other research projects. Research staff will
703 call these individuals twice (one week apart) and stop trying to contact these potential participants if these
704 phone calls do not go through. Additionally, they will do their best to confirm the identity of the potential
705 peer client before describing any details of the research study (and their potential participation in this
706 study).

707

708 Consenting procedures. *Peer providers.* All peer providers that meet eligibility requirements will provide

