709 written informed consent at the point of recruitment and prior to randomization with a trained research
710 assistant. This signed consent form will be stored as confirmation of informed consent and a copy will be
711 made available to the participant.

712 *Peer clients.* All peer clients that have contacted the study team directly, expressed interest in the study,
713 and have met eligibility requirements will complete informed consent at the Month 3 follow-up visit, before
714 completing any questionnaires assessing their experience with the peer PrEP referral + HIVST
715 intervention or informal peer PrEP referral process. Those unable or unwilling to come to the PHRD site
716 to sign a consent form will have the option to provide verbal consent over the phone. If verbal consent
717 was provided, the trained research assistant will note the date that verbal consent was obtained on a
718 copy of the consent script. The signed consent form and scripts will be stored as confirmation of informed
719 consent. A subset of peer clients who sign the written consent form will also be asked to provide a DBS
720 sample collected from a finger prick or venous blood. No peer client providing verbal consent will be
721 asked to provide a DBS sample.

722

723

Table 6. Eligibility and recruitment strategies- randomized trial

	Eligibility	Ineligibility	Recruitment Strategies
Peer providers (formerly “PrEP users”) (n=80)	
 • ≥ 16- 24 years old³⁶ • Female • Must have refilled or initiated PrEP (i.e., been dispensed PrEP) • Not currently enrolled in an HIV study • Can identify 4 peers at HIV risk who could benefit from PrEP • Able & willing to be randomized to the intervention, participate in research activities, and/or provide written informed consent 	
 • Not between 16-24 years old • Male • Have not used PrEP • Cannot identify 4 peers who would benefit from PrEP • Is not able or willing to be randomized to the intervention, participate in research activities, and/or provide written informed consent • Currently enrolled in an HIV study • Illiterate 	
 • Recruit participants from HIV clinics where PrEP is available using PHRD recruitment strategies (e.g., workshops for healthcare workers) • Strategies developed and refined during the pilot study

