Peer clients (formerly “peers”) (n=320)	
 • Age ≥ 16 to 24 years • Female • Referred by peer provider (i.e., a “PrEP user”) to initiate PrEP • Able & willing to provide informed consent 	
 • Age < 16 or > 24 years • Male • Not referred by peer provider (i.e., a PrEP users) to initiate PrEP • Not able and willing to provide informed consent 	
 • Peer providers will recruit peer clients. At point of recruitment, peer clients will call research staff to provide contact info for follow-up • At follow-up, peer providers share the contact information of peer clients so they can be reached for follow-up. • If peer client calls the study staff, both the peer client and provider will be compensated 150 KES via mobile money.

724

725

Randomization

726

727

728

729

730

Shortly after trial enrollment, peer providers will open in the presence of a study RA an opaque sealed envelope sequentially distributed to them that has their randomization arm specified inside (e.g., formal peer PrEP referral + HIVST arm; informal peer PrEP referral arm).

Study procedures & intervention

731

732

Depending on the arm peer providers are randomized to, the following procedures will apply (**Table 7, and Figure 7**):

Table 7. Interventions/materials received by peer providers and peer clients in the intervention and control arms

Intervention/material	Intervention arm		Control arm	
	Peer provider	Peer client	Peer provider	Peer client
Formal 1-day training on PrEP & HVIST	X			
Formalized conversation about PrEP, HIVST & referral	X	X		
PrEP educational brochure	X	X		
HIVST kits for distribution/self-testing	X	X		
WhatsApp group for questions	X			
PrEP referral card	X	X	X	X
Informal conversation about PrEP & referral			X	X

733

734

735

736

737

738

739

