## 3. Study overview and objectives

### 3.1. Study overview

**Table 1. Overview of the Peer PrEP cRCT components**

[figure not shown]
Protocol title:	Peer PrEP referral + HIV self-test delivery for PrEP initiation among young Kenyan women: randomized implementation trial
Short title:	Peer PrEP Study
Design:	This study is a hybrid effectiveness-implementation randomized trial
Population:	We will enroll two different population types in this study: 1. Index peers : (Also called PrEP users or peer providers in our formative research and pilot study). Adolescent girls and young women ≥16-24 years  old using PrEP for at least one month in the past 12 months.

	
2. Referred peers: (Also called peers or PrEP clients in our formative research and pilot study). Female peers <math>\geq 16</math>-24 years old of the index peer whom the index peer thinks has behaviors associated with HIV risk and may be interested in and benefit from daily oral PrEP.
 
16- and 17-year-olds must be emancipated minors; all participants must be able and willing to provide informed consent.

Randomization:	1:1 enhanced group: standard group

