Study groups:	
Intervention: Enhanced peer referral (previously formal peer referral)
 
 
• Index peers randomized to the enhanced group will receive the package of implementation strategies below and be encouraged to refer four peers to PrEP: 
 
○ A one-day training on HIVST & PrEP and how to have conversations about and refer peers to PrEP service
 
○ PrEP informational brochures (n=4, 1 per peer)
 
○ HIVST kits (n=8, 2 per peer)
 
○ PrEP referral cards (MOH-style), with information on nearby facilities delivering free PrEP services (n=4, 1 per peer)
 
 
 
• Referred peers referred to PrEP services by index peers in this group should receive the described package of implementation strategies to support PrEP referral.
 
 
Control: Standard peer referral (previously informal peer referral):
 
 
• Index peers randomized to the standard group will be encouraged to refer four peers to PrEP services using existing informal word-of-mouth referral, common among AGYW. They will receive: 
 
○ PrEP referral cards (MOH-style), with information on nearby facilities delivering free PrEP services (n=4, 1 per peer)
 
 
 
• Referred peers referred to PrEP services by index peers in this group will be referred to PrEP services informally, as is ongoing in Kenya.
 

Sample size:	
400 enrolled index and referred peers in total*
 
 
• 80 index peers
 
• Up to 320 referred peers
 
 
*The enrollment numbers for referred peers may be lower due to challenges in getting provide their contact information at the time of peer referral. Primary outcomes among referred peers will be reported by index peers in index peer follow-up surveys.

Follow-up:	3 months from either the time of intervention delivery (index peers) or time when study staff received their contact information (referred peers)
Study sites:	Three counties in Central Kenya: Kiambu, Nairobi, and Murang'a (in the area surrounding the PHRD research clinic in Thika)

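### A single block size of 4, with envelopes opened in sequence in front of site staff, makes an expected one-third of allocations predictable to anyone who knows or infers the block size

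*SAP*

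**What the plan says.** SAP 6.1 states that a statistician at the coordinating centre "will prepare a list of randomization assignments for index peers with block sizes of 4". It gives no other block size and no stratification factor. SAP Table 1 gives the ratio as "1:1 enhanced group: standard group" and the number randomised as "80 index peers". The list is kept in a password-protected file on the coordinating centre's server.

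On implementation, the Protocol (Aim 2, Randomization) says that "peer providers will open in the presence of a study RA an opaque sealed envelope sequentially distributed to them". SAP 6.1 says that "index peers will open an opaque randomization envelope, given to them by a study research assistant". The Protocol's recruitment text adds: "Recruitment of peer providers will be on a rolling basis". Its consent text has index peers give "written informed consent at the point of recruitment and prior to randomization", with a trained research assistant.

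The arms cannot be concealed from the site. Protocol Table 7 gives the training, the self-test kits, the brochure and the WhatsApp group to the intervention arm only.

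Neither document says that the block size is withheld from site staff. Neither says that the staff who enrol are different from those who see envelopes opened.

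**The concern.** Sealed opaque envelopes stop anyone from reading the next assignment. They do not stop anyone from deducing it from the assignments already seen. When every block holds exactly two of each arm, the end of a block follows from its start.

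The step matters more here than in many trials. The index peer is the randomised unit. She chooses the referred peers after she learns her arm, and her report at Month 3 is the primary outcome. If the timing of an index peer's enrolment depended on a foreseeable assignment, the arms could differ in how motivated or well connected their index peers are, and that difference would pass straight into the primary contrast. The model in SAP 10.2 contains study group and an index-peer random effect, with no baseline covariates. None of the sensitivity analyses in SAP 10.4 addresses selection at enrolment.

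There is some room for discretion. The Protocol describes several recruitment routes, and eligibility includes judgements such as literacy and the ability to name four peers at risk.

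**Working it through.** **The plan's own figures.** Neither document states how predictable allocation is, so there is no such figure to reproduce. The planning power in SAP 5.1 does reproduce. With 120 referred peers per arm and a design effect of 1 + 2 × 0.05 = 1.10, the effective size is 120/1.10 = 109.1 per arm. Power for 63% versus 80% is then 79.9%, against the stated 80%. This point does not alter that figure.

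**Inputs.** Block size 4 (SAP 6.1); 1:1 ratio and 80 index peers (SAP Table 1), so 80/4 = 20 blocks of 2:2; one unstratified list used in order (SAP 6.1 and Protocol, Randomization). The observer is assumed to know the block size and all earlier assignments.

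**Certain allocations in one block.** A 2:2 block has 6 equally likely orders.

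| Position | Probability that the arm is certain beforehand | Probability that the best guess is right |
|---|---|---|
| 1 | 0 | 1/2 |
| 2 | 0 | 2/3 |
| 3 | 2/6 = 1/3 (first two alike) | 1/3 × 1 + 2/3 × 1/2 = 2/3 |
| 4 | 1 | 1 |
| Sum | 4/3 | 17/6 |

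- Certain share: (4/3)/4 = 33.3%.
- Best-guess accuracy: (17/6)/4 = 70.8%, against 50% by chance.

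**Over 20 blocks.** Each block contributes one certain allocation, plus a second with probability 1/3 from the early-match case. The total is 20 + Binomial(20, 1/3).
- Expected: 20 + 20/3 = 26.7 of 80.
- Central 95% range: 23 to 31.
- Minimum 20 (25%); maximum 40 (50%).

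**Other schemes.** Fixed blocks were enumerated. Varying blocks were simulated over 80 allocations, with an observer who knows which sizes are possible but not their order, and who updates by Bayes' rule.

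| Scheme | Certain in advance | Best guess right |
|---|---|---|
| Fixed 4 | 33.3% | 70.8% |
| Fixed 6 | 25.0% | 68.3% |
| Fixed 8 | 20.0% | 66.6% |
| Random 4 or 6 | about 5.6% | about 69.1% |
| Random 4, 6 or 8 | about 2.4% (about 2 of 80) | about 67.9% |

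Varying the size nearly removes certainty. It does much less against informed guessing: the excess over chance falls from 20.8 to 17.9 points.

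**The case against.** The strongest reply is that the one-third figure is conditional. It needs someone who knows or infers that blocks are of size 4 and who has tallied every earlier envelope. The block size appears in the SAP and not in the Protocol's randomization text, and the list is held off site. Both documents refer to a research assistant without saying that one person sees the whole sequence or controls the order of enrolment. Nothing shows that the healthcare workers and community health workers who help to find candidates see any assignment. Steering also needs spare candidates, and the Protocol reports difficulty recruiting index peers in the pilot.

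All of this stands as a limit on what can be concluded. It does not remove the weakness. Nothing says that the size is withheld, and exact balance after every fourth envelope is not hard to notice. The same staff role takes consent and attends the envelope opening, with no stated separation. Consent before randomisation does not help, because a prediction can be formed before the next candidate is approached.

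A reader might go further and infer that the primary result is biased, or turn the one-third share into a bias in percentage points. The documents support neither step. They contain no evidence of steering and no figure for how index peers would differ if it happened, so any bias size would rest on an invented input.

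It is also fair to say that a new list may come too late. SAP Table 2's footnote places November 2023 at six months into the trial, and SAP Table 3's footnotes record outcome revisions in March and July 2024. Neither document states whether enrolment has closed.

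**Conclusion.** The point holds as a preventable weakness in allocation concealment. For an observer who knows or infers the block size and tracks the sequence, an expected 26.7 of 80 allocations are certain in advance (95% range 23 to 31, never below 20), and the best guess is right 70.8% of the time. These figures are exact for one unstratified 2:2 list with blocks of 4 used in order, which is how the documents read.

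Whether anyone at the site was in a position to use this is not stated. No bias has been shown, and its size cannot be estimated from the documents. The change is a cheap improvement and not a condition for the trial's validity.

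**What to change.** **If envelopes remain unused.** In SAP 6.1, replace the single block size for the remaining list with randomly varying sizes (for example 4, 6 and 8), held by the off-site statistician and not disclosed to the site. The cost is one new list, one SAP sentence and a possible small imbalance in final arm sizes: stopping inside a block of 8 can leave the arms at most 8/2 = 4 index peers apart. The benefit is mainly the removal of certainty.

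Opening envelopes in batches may look natural because training is done in groups, but only intervention-arm index peers are trained. Batching would make control participants wait or return, so it is not proposed.

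**If enrolment is complete.** Two additions cost only reporting and a short analysis:

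1. State the block size in the trial report, who knew it, and whether the staff who enrolled also saw envelopes opened.
2. Add a sensitivity check to SAP 10.4. Classify each index peer as predictable (position 4, or position 3 after two like assignments) or unpredictable. Compare index-peer baseline characteristics by arm within each class, and compare the primary effect between classes.

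The check will be imprecise, with about 26.7/2 = 13 predictable index peers per arm expected. It can reveal selection on measured traits, but it cannot fully correct selection or exclude it on unmeasured ones.
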